3.2 INCLUSION / EXCLUSION CRITERIA

3.2.1 Inclusion criteria:

Individuals over 50 years of age referred for colonoscopy under any indication.

Over 60 years of age,

Change in bowel habit to looser/more frequent stools,

+/- PR bleeding AND

2 positive FIT/FOB tests.

3.2.1 Exclusion criteria:

a) Need for emergency surgery,

b) Presence of Inflammatory bowel disease,

c) Known history of inherited colorectal cancer,

d) History of cancer in another primary site,

e) Presence of liver metastases (Neurotensin is metabolized in the liver),

f) Negative previous colonoscopy for cancer,

g) Haemolysis in serum samples,

h) Informed consent not signed/withdrawal and

i) Persons who will not have the capacity to decide for

themselves, who are unable to represent their own interests or are particularly susceptible to coercion.

Information concerning performance status, use of statins, steroids or any

anti-inflammatory / immunosuppressive medications will also be collected.

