1.2 TITLE OF THE STUDY

The combined use of serum Neurotensin and IL-8 as screening markers for

colorectal cancer and adenomas. A prospective study.

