1.8 THE NEED FOR A TRIAL

Colorectal cancer mortality can be lowered by both early diagnosis and cancer prevention.[1, 2] The objective of screening is to detect cancer at an early, curable stage. Individuals at average risk, those older than 50 years of age, with a negative family history and negative history of adenoma, colorectal cancer, or inflammatory bowel disease are among the highest yield group.

Recent literature proposes that after an initial negative colonoscopy (which is the current standard of screening not only in average risk but also in increased risk patients, should start at age 50 or earlier age with frequency depending on risk factors: e.g. personal/family history of polyps/cancer, inflammatory bowel disease, known genetic syndrome and prior colonoscopy findings), follow-up with rescreening after the age of 60 with annual guaiac fecal occult blood testing, annual fecal immunochemical testing, or computed tomographic colonography every five years provides approximately the same benefit in life-years with fewer complications and at a lower cost.[3] There is a lack of consensus concerning the use of CT colonography as a primary screening tool.

The number of CRC cases from colorectal cancer screening is still rather low. Sensitivity of guaiac tests for the detection of CRC/adenomas is 21.8%-46.3%.(4) Colonoscopy is the favoured screening method for individuals at average risk despite lower patient compliance with this modality. A meta-analysis of 14 randomized controlled trials documented that although endoscopic surveillance was superior to stool testing in detecting advanced neoplasms, its benefit was eclipsed by a lower participation rate.[4] Colonoscopy is the favored screening method for individuals at average risk despite lower patient compliance with this modality. Whilst colonoscopy is an outstanding tool for diagnosing potentially curable bowel cancer, too many patients are currently having an unnecessary procedure as the pick-up rate for bowel cancer is only 4%. Nevertheless, NCCN guideline panelists agree that any form of screening is better than none.[5]

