An actual connection between the proposed screening markers and the detection of colorectal cancer and adenomas would have a significant impact on: a) target population compliance, b) re-definition of the cancer pathway for candidate patients by changing the indications for colonoscopy and c) the cost-effectiveness, vital for patients' survival and the sustainability of the NHS, by means of earlier cancer/adenoma diagnosis.

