2. INTRODUCTION

Cancer research offers a better insight into regulatory mechanisms involved in cell proliferation in colorectal cancer, and might eventually guide us to new possibilities in terms of novel biomarkers that would facilitate early diagnosis.

Neurotensin (NT) mediates its effects by binding to three neurotensin receptors NTSR-1, -2, and -3: the first two are G-protein coupled receptors, whereas the third belongs to the sortilin receptor superfamily. [6-8] NT via NTSR-1 initiates a multiplicity of intracellular signaling pathways in colon cancer cells and in non-transformed NCM460 colonocytes, as well as the epidermal growth factor receptor (EGFR) and downstream mitogenactivated protein kinases (MAPK) via the metalloproteinase-dependent cleavage of pro- TGF alpha.[9] NT-mediated activation of MAPK signaling and the downstream transcription factor activator protein 1 (AP1) also occurs rapidly in human colorectal cell lines.[10] Moreover, transactivation of the IL-8 promoter is triggered by NT-mediated AP1 activation [10, 11] while NT also stimulates Ras pathway and nuclear factor kappa-light-chain-enhancer of activated B cells (NF-kB) -dependent secretion of IL-8.[6, 12] Intense transcription of the NTSR-1 gene via TCF/Lef- and nuclear β-catenindependent pathways can explain NTSR-1 overexpression in colon cancer.[13] Higher NT levels are also obtained from colon cancers compared to normal colon tissues, and in vivo evidence establishes that NT/NTSR-1 signaling is fundamental for tumor growth.[14]

Gui et al [15] found that NTSR1 expression was considerably increased in both adenomas and adenocarcinomas compared with histologically normal epithelium and in adenocarcinomas compared with adenomas.

Given that colorectal cancer is the second leading cause of cancer-related death in Europe and the third in the USA, a new non-invasive screening modality with the potential for high population compliance at a lower cost than the current screening system and with the capacity for early detection of

colorectal cancer and precursor adenomatous polyps is of paramount importance.[16, 17]

This pilot study aims to investigate whether specific pattern of serum neurotensin/NTSR1/IL-8 values can detect patients with adenomas or colorectal cancer and determine the feasibility of these agents being used as a screening tool.

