4.4 Subgroup analyses

All analyses mentioned above are also performed stratified by gender, BMI and ethnic background respectively.

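### The markers are presented for screening, but the primary cut-offs and AUC come only from people referred for colonoscopy, and the protocol does not limit their transfer to an unreferred population

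*Protocol*

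**What the plan says.** - **Aim.** The title (1.2) begins "The combined use of serum Neurotensin and IL-8 as screening markers for" colorectal cancer and adenomas. The Introduction (section 2) calls the study a pilot that is to "determine the feasibility of these agents being used as a screening tool". Section 3 promises participants a letter on the findings and what they may mean for future bowel cancer screening.
- **Rationale.** Section 1.8 discusses "Individuals at average risk, those older than 50 years of age, with a negative family history and negative history of adenoma, colorectal cancer". The same description also rules out inflammatory bowel disease, and the section places this group among those with the highest yield. It also lists a second use, "re-definition of the cancer pathway for candidate patients by changing the indications for colonoscopy".
- **Enrolment.** Section 3.2 takes "Individuals over 50 years of age referred for colonoscopy under any indication". It then lists age over 60, looser or more frequent stools, with or without rectal bleeding, and two positive FIT/FOB tests, without saying how these lines combine with the first. Exclusion "f) Negative previous colonoscopy for cancer" carries no time limit.
- **Analysis.** Section 3.1 sets cut-offs from cancer versus normal colonoscopy and from adenoma versus normal colonoscopy, and uses the normal group to define the normal range. Section 3.3 makes the cut-offs and AUC primary. Section 3.4 speaks of matched population controls.
- **Strata.** Section 4.4 reads "All analyses mentioned above are also performed stratified by gender, BMI and ethnic background respectively". Referral indication is not among them.

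**The concern.** A cut-off and an AUC describe the cases and controls from which they were estimated. Here both come from people already selected for colonoscopy, in an unstated mix of symptomatic, stool-test-positive and other referrals. The controls also had a reason to be referred, so their marker values need not match those of unreferred people. If marker levels differ by indication, one pooled estimate partly reflects the referral mix at two hospitals.

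At stake is what the trial may conclude. Nothing in the protocol confines the cut-offs or AUC to referred patients or plans their validation in unreferred people, while the title and the promised letter speak of screening. A reader would naturally take the result as screening performance.

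**Working it through.** **1. Population described and population enrolled**

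| Feature | Section 1.8, average risk | Section 3.2, enrolled |
|---|---|---|
| Route | Screening | Referred for colonoscopy, any indication |
| Symptoms, stool test | Not part of the description | Bowel symptoms and two positive FIT/FOB tests listed |
| Family history | Negative | Only known inherited colorectal cancer excluded |
| Inflammatory bowel disease | None | Excluded |
| Earlier negative colonoscopy | Non-invasive rescreening described from the literature | Excluded, no time limit |

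The two agree on inflammatory bowel disease and partly on family history. They differ on route, symptoms and earlier colonoscopy.

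**2. Why the estimates depend on the mix**

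Let indication k supply a share w_k of the cases and v_k of the controls. At cut-off c:

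- pooled sensitivity(c) = Σ w_k × sensitivity_k(c)
- pooled specificity(c) = Σ v_k × specificity_k(c)
- pooled AUC = Σ_j Σ_k w_j v_k × AUC_jk, with cases from j and controls from k

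The pooled values are free of the mix only if the markers behave alike in every indication. The documents give no accuracy by indication, so the size and direction of any shift cannot be computed.

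**3. The protocol's own sample size (section 3.5)**

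Inputs: AUC 0.85, 95% interval of total width 0.1 (half-width 0.05), prevalence 20% to 30%, binormal ROC curve. Obuchowski variance, with R = controls per case:

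- A = 1.414 × z(0.85) = 1.414 × 1.036 = 1.466, so A² = 2.148
- V = 0.0099 × exp(−A²/2) × [(5A² + 8) + (A² + 8)/R]
- 20% (R = 4): V = 0.003383 × (18.74 + 2.54) = 0.0720. Cases = 1.96² × 0.0720/0.05² = 110.6. N = 110.6/0.20 = 553.
- 30% (R = 2.33): V = 0.003383 × (18.74 + 4.35) = 0.0781. Cases = 120.0. N = 120.0/0.30 = 400 (401 if rounded up).

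The stated 400 and 553 reproduce, so the sample-size arithmetic is not at fault.

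**4. What a split by indication can deliver with 500 participants**

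- Adenoma or cancer: 500 × 0.20 = 100 to 500 × 0.30 = 150.
- Cancers, if the 4% pick-up in section 1.8 applies: 500 × 0.04 = 20. That leaves 80 to 130 adenomas.
- Interval for the cancer AUC before any split: with 20 cases and 480 others, R = 24 and V = 0.0648, so the width is 2 × 1.96 × √(0.0648/20) = 0.22. With only the 350 to 400 normal colonoscopies as controls it is still 0.22.
- Split evenly over three indications (an assumption), 20 cancers give about 7 each.

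**5. Illustration of lower prevalence, neurotensin alone**

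Pilot sensitivity 77% and specificity 90% (section 2.1.1), both held constant: PPV = 0.77p / [0.77p + 0.10(1 − p)].

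| Prevalence p | Source | PPV |
|---|---|---|
| 4% | Section 1.8 | 0.0308/0.1268 = 24.3% |
| 1% | Assumed | 0.0077/0.1067 = 7.2% |
| 0.5% | Assumed | 0.00385/0.10335 = 3.7% |
| 0.3% | Assumed | 0.00231/0.10201 = 2.3% |

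Because sensitivity and specificity are fixed, the table shows prevalence alone. It does not measure bias in the AUC or the cut-offs.

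**The case against.** The protocol makes modest claims. It calls itself a feasibility pilot, section 5.5 makes a multicentre study the next step if results are promising, and section 3 says participants' care will not be affected. Section 1.8 does not restrict the markers to average-risk people. It reports rescreening after a negative colonoscopy as a literature finding about other tests, not as a planned use of these markers. The second use, deciding who needs colonoscopy, suits a referred cohort, and colonoscopy is the reference standard that assigns the groups. Exclusions (b) and (c) move the cohort towards average risk, and the any-indication line may admit screening referrals. Sections 3.1 and 4.2 already plan a comparison with the two-week referral and FOB route. The PPV table ignores the two-step rule in section 2.1.1, under which none of the 13 pilot cancers was missed.

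All of this stands, and it narrows the point. A reader might infer that the markers are claimed only for average-risk people and that the study can say nothing about screening. The documents support neither inference. What remains unanswered is that no section states the limit on transfer, and that the planned comparison with the referral/FOB route does not report the markers' own accuracy by indication. Analysis detail may be left to a SAP, but section 4.4 already fixes a list of strata and omits the one that bears on the aim.

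**Conclusion.** The point holds as a gap in applicability. The primary cut-offs, AUC and normal range describe people over 50 referred for colonoscopy without an earlier negative one. They cannot be carried to an unreferred screening population without validation there, and the protocol should say so. This should be corrected, but it does not invalidate the study for its feasibility aim or for deciding who needs colonoscopy.

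The size of any shift in AUC or cut-off is unknown from the documents. The fall in PPV from 24% to between 7% and 2% rests on assumed prevalences of 1% to 0.3%, on constant sensitivity and specificity, and on neurotensin alone. A reader might take those figures as the bias in the primary endpoints, which they are not. The count of about 20 cancers assumes that the 4% pick-up applies to this cohort.

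**What to change.** 1. **Objective and conclusion.** State that the cut-offs and AUC apply to people referred for colonoscopy, in line with the use of deciding who needs one, and that screening use requires validation in an unreferred population. Word the participants' letter the same way. Cost: wording and a narrower claim.
2. **Referral indication.** Record it for every participant from the GP referral, which section 3 already names as a data source. Add it to the strata in section 4.4 and report AUC, sensitivity and specificity by indication as exploratory. Cost: one variable, with no extra patients, visits or assays. Intervals will be wide and the cancer strata sparse, so the split will be usable mainly for adenomas.
3. **Reconciliation.** Say how the two sets of inclusion lines in section 3.2 combine, and reconcile the population controls of section 3.4 with the in-cohort controls of section 3.1. These choices decide how symptomatic the cases and controls are. Cost: a clarification, best made before enrolment.
4. **Predictive values.** If shown, give the assumed prevalence beside each one and state that sensitivity and specificity were held constant.

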3. STUDY DESIGN ASPECTS

We consider sending Participant Information Sheet (PIS) about the present study to patients due to have colonoscopy via regular mail along with their appointment letter. Research Nurses are already available on both sides will inform and consent patients for blood sampling. We consider let all participants know about the analysis of results of this study. A letter will be

sent with the main findings and the potential implications for the future of the bowel cancer screening.

Blood sample will be Centrifuged and serum will be kept frozen at -80°C in both hospital sites until it will be transferred to the Biomedical and Life Sciences, Lancaster University for ELISA measurement.

Each Participant will be explained the objectives of the study, will sign the consent form for participation and will be cannulated for colonoscopy (the vast majority of patients undergoing colonoscopy wish to have sedation/analgesia) and blood will be drawn from the cannula before the administration of the sedation/analgesia for their colonoscopy.

Two of the investigators ([name] and [name] will be involved in participants colonoscopy.

Participant data or samples will be identified by the unique study number. Participants will not be referred to a separate research team and the arrangements for identification and referral will be kept strictly to the participating trusts. The aforementioned information will be explained clearly in the letter of invitation and/ or written information for participants. In the occasional case that we will recruit prisoners, their GP will receive all the necessary information.

The initial approach to potential participants should be made by a member of the healthcare team responsible for patients' colonoscopy as it is normally done in the endoscopy unit. The research Nurse will be present as well in order to inform and consent patient for the taking of the blood sample. The identification of potential participants will not involve reviewing or screening the identifiable personal information. Research will entail the taking

participant blood, measurement of biomarkers and statistical analysis to document their predictive value. There will not be any direct or indirect clinical implication to participant health care management.

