3.1 CONTROL(S) / COMPARATOR(S)

All individuals fulfilling the inclusion criteria will be enrolled. After the refinement of participants by the exclusion criteria blood sample will be drawn for Neurotensin and IL-8. Following the report of colonoscopy and the histology individuals will be assigned in three groups: a) group A - cancer patients, b) group B – adenoma (polyp) patients and c) group C – No pathology/normal colonoscopy. Two primary analyses will be conducted to define the cut-off plasma values for Neurotensin and IL-8 for a) diagnosing cancer (group A versus group C) and b) diagnosing adenomas (group B versus group C). A secondary analysis will be conducted comparing the performance of the Neurotensin/IL-8 system towards the 2-weeks referral and FOB test positive patients for the diagnosis of colorectal cancer and adenomas.

The reason for using participants without bowel pathology is because we need to define the "normal range" of Neurotensin and IL-8 serum values.

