4.2 Exploratory analysis of secondary endpoints

Adenoma frequency and other qualitative characteristics: H0: p1=p2 is tested against the alternative H1: $p1 \neq p2$.

The diagnostic performance of the proposed biomarker system of Neurotensin and IL-8, will be assessed against the current screening system with 2-weeks referral/FOB test by using propensity scoring in binary logistic regression.

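### The inclusion list gives two incompatible entry rules; the secondary comparison with FOB is degenerate under one and selection-biased under the other

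*Protocol*

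**What the plan says.** Protocol 3.2 lists, under one heading for inclusion:

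- "Individuals over 50 years of age referred for colonoscopy under any indication"
- "Over 60 years of age"
- "Change in bowel habit to looser/more frequent stools", with or without rectal bleeding, joined by a capitalised AND to
- "2 positive FIT/FOB tests"

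No word says whether the later lines restrict the first line, are an alternative to it, or only describe one type of referral. Section 3.1 adds: "All individuals fulfilling the inclusion criteria will be enrolled". Section 3 says that invitations go to "patients due to have colonoscopy via regular mail along with their appointment letter".

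Section 3.1 plans a secondary analysis "comparing the performance of the Neurotensin/IL-8 system towards the 2-weeks referral and FOB test positive patients". Section 4.2, on exploratory analysis of secondary endpoints, fixes the method: the marker system "will be assessed against the current screening system with 2-weeks referral/FOB test by using propensity scoring in binary logistic regression".

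**The concern.** Two questions follow from this text.

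**Who is enrolled.** Two sites recruit, and all who qualify are to be enrolled. One site could take anyone over 50 booked for colonoscopy. The other could take only patients over 60 with symptoms and two positive stool tests. These are different populations.

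**What the comparison with current practice means.** The comparator in 3.1 and 4.2 is a referral and stool-test pathway. Under the narrow rule a positive result on that stool test is itself a condition of entry. Under the broad rule patients are in the study because some pathway sent them for colonoscopy. In both cases the comparator helps decide who is observed. Section 1.8 hopes that the markers will change the indications for colonoscopy, and this is the analysis a reader would turn to for that claim.

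**Working it through.** **Step 1: the inclusion lines side by side.**

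| Reading | Effect on the first line | Effect on the later lines |
|---|---|---|
| All lines must hold | Void: over 60 overrides over 50, and the stool tests override any indication | Define the cohort |
| Either block suffices | Defines the cohort | Redundant: a patient over 60 who is booked for colonoscopy already meets the first line |
| Later lines are an example of an indication | Defines the cohort | No effect on eligibility |

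Recruitment is from patients already booked for colonoscopy (Section 3), so on no reading do both blocks do work.

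**Step 2: the comparator under each rule.** Let Se and Sp be the true sensitivity and specificity of FOB. Let r be the chance that a FOB-negative person reaches colonoscopy, relative to a FOB-positive person, taken as equal in those with and without disease. Then, among enrolled patients:

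- apparent sensitivity = Se / (Se + (1 − Se) × r)
- apparent specificity = Sp × r / (Sp × r + 1 − Sp)

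Inputs: Se = 21.8% and 46.3%, the guaiac range in Section 1.8. Sp = 95% and the values of r are assumptions made for illustration; the protocol gives neither.

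*Narrow rule, r = 0.* Sensitivity = Se / Se = 100%. Specificity = 0 / (1 − Sp) = 0%. This holds for any Se above 0 and any Sp below 1, so it needs no assumed figure.

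*Broad rule, r > 0.* Worked example at r = 0.2:

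- 0.218 / (0.218 + 0.782 × 0.2) = 0.218 / 0.3744 = 58%
- 0.463 / (0.463 + 0.537 × 0.2) = 0.463 / 0.5704 = 81%
- specificity: 0.95 × 0.2 / (0.19 + 0.05) = 0.19 / 0.24 = 79%

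| r (assumed) | Apparent sensitivity (Se 21.8% to 46.3%) | Apparent specificity (Sp 95%) |
|---|---|---|
| 0 | 100% | 0% |
| 0.05 | 85% to 95% | 49% |
| 0.2 | 58% to 81% | 79% |
| 0.5 | 36% to 63% | 91% |
| 1 | 21.8% to 46.3% | 95% |

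Only at r = 1, where FOB result plays no part in referral, do the true values return.

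**Step 3: the method named in 4.2.** Propensity scores balance measured covariates between groups of enrolled patients. They cannot supply people who were never referred. Nor do they compare two tests applied to the same patients, which is the natural question when each participant has marker values, colonoscopy and perhaps a stool test.

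**Step 4: the sample size.** Section 3.5 uses AUC 0.85, a 95% interval of width 0.1 and the binormal form. With A = 1.414 × z(0.85) and k controls per case:

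- V = 0.0099 × exp(−A²/2) × [5A² + 8 + (A² + 8)/k]
- cases = 1.96² × V / 0.05²; N = cases / prevalence

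At 30% prevalence this gives 120.0 cases and N = 400.0. At 20% it gives 110.6 cases and N = 552.9. The protocol's 400 and 553 reproduce. Eligibility enters only through the assumed prevalence.

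**The case against.** The strongest reply concerns the broad rule. If any indication qualifies, patients may come by routes other than two-week referral or a positive stool test; Section 1.8 names family history and earlier findings among the risk factors that set screening frequency. Every participant has colonoscopy, so comparator-negative patients in the cohort are verified. A reader might infer that the comparison cannot be estimated whichever rule is meant. The documents do not support that. Under the broad rule the yield by referral route, marker accuracy among referred or FOB-positive patients, and a within-cohort contrast can all be computed. What cannot be had without selection bias is the accuracy of the current pathway in unreferred people.

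A reader might also infer that the two rules move the required sample size to 400, 553 or, at 4% prevalence, about 2,490. That does not stand either. The 20% to 30% in 3.5 is one planning range for adenoma and cancer together, and no section ties a point in it to either rule. The 4% in Section 1.8 is a pick-up rate for bowel cancer alone.

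Two further replies have some weight. The comparison is exploratory, and the loose wording of 3.1 could mean only testing the markers among FOB-positive patients, which is feasible. But 4.2 says that the assessment is against the current screening system and fixes the method, so this is not a detail left to a later plan.

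**Conclusion.** The inclusion list contradicts itself and must be reconciled; that part rests on the text alone. Which rule applies is for the sponsor to decide.

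The consequence for the secondary comparison depends on the rule:

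- **Two positive FIT/FOB tests required of all:** FOB has no variation (sensitivity 100%, specificity 0%), and the comparison with it is degenerate. This is shown for the stool test only; two-week referral is not itself named as an entry condition.
- **Any indication:** the comparison can be computed, but it is selection-biased and does not carry over to screening. The size of the bias is unknown. The figures above rest on an assumed specificity, assumed referral ratios, and equal referral in people with and without disease.

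The two primary analyses (cancer versus normal, adenoma versus normal) do not use this comparison. The point should be corrected, but it does not overturn the main design.

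**What to change.** 1. State one inclusion rule in 3.2, and say how any remaining lines relate to it.
2. If two positive stool tests are required of everyone, remove the comparison with FOB from 3.1 and 4.2.
3. If any indication qualifies, record referral route and FIT/FOB result for each participant, from the GP referrals and hospital records that Section 3 already names as data sources.
4. Under the broad rule, replace the propensity-score comparison in 4.2 with a within-cohort analysis by referral route: the proportion of cancers and of adenomas detected, and the proportion of colonoscopies avoided, under the two-step neurotensin then IL-8 rule of 2.1.1. Where FIT/FOB results include both positives and negatives, compare the tests in the same patients with McNemar's test, separately in those with and without disease.
5. State that performance against two-week referral or FOB in an unreferred screening population cannot be concluded.

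The cost is protocol wording and, under the broad rule, two recorded variables. The sponsor gives up an exploratory head-to-head claim against the current screening system, which these data could not support.

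### The exclusion criteria leave out previously treated sporadic colorectal cancer, so such patients can enter group C, the comparator that defines normal

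*Protocol*

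**What the plan says.** Protocol section 3.2 opens eligibility to "Individuals over 50 years of age referred for colonoscopy under any indication". The exclusions that bear on cancer history are:

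- "c) Known history of inherited colorectal cancer"
- "d) History of cancer in another primary site"
- "f) Negative previous colonoscopy for cancer"

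Criterion (e) also removes people with liver metastases.

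Section 3.1 forms the three groups from the report of the study colonoscopy and its histology. The comparator is "group C – No pathology/normal colonoscopy", and no condition on past history is attached. Group C serves as comparator for cancer (A versus C) and for adenoma (B versus C). Its purpose is stated: "The reason for using participants without bowel pathology is because we need to define the 'normal range' of Neurotensin and IL-8 serum values".

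As background, section 1.8 describes average-risk people as those "with a negative family history and negative history of adenoma, colorectal cancer, or inflammatory bowel disease are among the highest yield group". The same section lists a personal history of polyps or cancer among the factors that govern how often colonoscopy is done, so the protocol recognises that such patients are referred.

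**The concern.** A comparator meant to show normal serum values should not contain people whose values may reflect an earlier colorectal cancer. Resection, systemic treatment, or residual disease outside the bowel lumen could each affect the markers, and a clear colonoscopy does not rule these out. Such people are also not the undiagnosed population that the test is meant to triage.

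The primary endpoints in section 3.3 are the cut-offs and the AUC, and both primary contrasts use group C. The pilot in section 2.1.1, which supplies the AUC of 0.85 used for the sample size, took healthy people as controls.

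The problem may also be hard to undo at analysis. The additional information listed in section 3.2 covers performance status and certain medicines, but not previous colorectal cancer.

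**Working it through.** **1. Following one patient through the criteria.** Take a person over 50, treated for sporadic colorectal cancer, now referred for surveillance.

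| Criterion | Effect on this patient |
|---|---|
| Inclusion, first line | Admitted: any reason for colonoscopy suffices |
| (c) inherited colorectal cancer | Not excluded: the cancer was sporadic |
| (d) cancer at another site | Not excluded: the earlier cancer was colorectal |
| (e) liver metastases | Excluded only if they are present |
| (f) earlier colonoscopy clear of cancer | Excluded if there was one, before diagnosis or since treatment |
| Group assignment, section 3.1 | Recurrence goes to A, adenoma to B; a normal examination can go to C |

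The route is therefore open mainly at the first colonoscopy after treatment, for someone with no earlier examination clear of cancer.

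**2. The plan's own figure.** Section 3.5 assumes AUC 0.85, a 95% interval of total width 0.1 and prevalence of 20% to 30%, and arrives at 553 and 400 participants. The binormal variance is V = 0.0099·exp(−a²/2)·[(5a²+8) + (a²+8)/k], with a = 1.414·z(0.85) and k = (1−p)/p. Then n(cases) = 1.96²·V/0.05² and N = n(cases)/p.

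- p = 0.30: 120.0 cases, N = 400.0
- p = 0.20: 110.6 cases, N = 552.9

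Both figures reproduce. The eligibility gap does not affect them.

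**3. Possible size in group C.** With 500 participants, and everyone without adenoma or cancer placed in C, the group holds 500 × 0.70 = 350 to 500 × 0.80 = 400 people. The share f of treated patients is not given, so 2%, 5% and 10% are assumptions. They correspond to about 7–8, 18–20 and 35–40 people.

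**4. Illustration for A versus C.** Use an equal-variance binormal model with the marker oriented so that higher means more cancer-like (reversed for neurotensin). The separation is d = √2·z(0.85) = 1.466. Treated patients sit a fraction r of the way from normal to cancer levels.

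- AUC observed = (1−f)·0.85 + f·Φ((1−r)·d/√2)
- Specificity at the true 90% cut-off = (1−f)·0.90 + f·Φ(1.2816 − r·d)
- Youden cut-off: the value maximising sensitivity plus mixed specificity; without contamination it is d/2 = 0.733 SD

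| r | f | AUC | Specificity | Youden cut-off (SD) |
|---|---|---|---|---|
| 0 (normal) | any | 0.850 | 90.0% | 0.733 |
| 0.5 | 2% | 0.847 | 89.6% | 0.737 |
| 0.5 | 5% | 0.842 | 89.0% | 0.744 |
| 0.5 | 10% | 0.835 | 88.1% | 0.755 |
| 1 (as cancer) | 2% | 0.843 | 89.1% | 0.733 |
| 1 | 5% | 0.8325 | 87.6% | 0.733 |
| 1 | 10% | 0.815 | 85.3% | 0.733 |

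At r = 1 the AUC loss is f × (0.85 − 0.50) = 0.35f, or 0.007, 0.0175 and 0.035. Against the planned half-width of 0.05 these are 14%, 35% and 70%.

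The Youden cut-off does not move at r = 1 because the observed index is (1−f) times the true one, so its maximum stays in place. The largest shift in the table is 0.755 − 0.733 = 0.022 SD.

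Using the pilot neurotensin figures directly (sensitivity 77%, specificity 90%), the r = 1 specificity is (1−f)·0.90 + f·0.23, which gives 88.7%, 86.7% and 83.3%. This is lower than in the model because the pilot sensitivity at that cut-off exceeds the one the model implies.

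**The case against.** Several limits are fair, and most of them stand.

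- **What (f) does.** A reader might infer that (d) and (f) together turn away people with a clear history and take in cancer survivors generally. The text does not support that. Criterion (f) has no time limit, so it equally removes treated patients who have had any colonoscopy clear of cancer.
- **Other inclusion lines.** Section 3.2 also lists age over 60, altered bowel habit and two positive stool tests, without saying how these combine with the first line. If all were required, few surveillance patients would enter. That reading would make the first line's lower age and open indication redundant, so it is the less natural one, but it cannot be ruled out.
- **Entry to group C.** The protocol does not say whether a resected bowel counts as free of pathology.
- **Section 1.8.** A reader might see a contradiction with the criteria. It is background on average-risk screening, not an eligibility statement, and section 3.2 may choose a wider population.
- **Cut-offs.** A reader might infer that the cut-offs are distorted. The illustration does not show this for the Youden rule. The protocol names no rule for choosing a cut-off from the ROC curve, so other rules are untested here.
- **Size.** The 10% row needs 35–40 treated patients in group C, all with cancer-like markers. If only a few qualify, the effect is near the 2% row or below.

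These points narrow the route and its likely effect. They do not close it: no criterion addresses a personal history of sporadic colorectal cancer, and group C carries no history condition.

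**Conclusion.** The eligibility rule, as worded, can place treated colorectal cancer patients in the group that defines normal and anchors both primary ROC analyses. This may bias the AUC and the apparent specificity. The size is unknown and could be nil.

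If treated patients make up 2% to 10% of group C and their markers are fully cancer-like, a true AUC of 0.85 would read about 0.84 to 0.82, with little movement of the Youden cut-off. That is an upper bound for those shares, provided treated patients' markers lie somewhere between normal and cancer levels. Neither the shares nor the marker levels come from the protocol. The figures concern A versus C; the protocol gives no pilot AUC for adenoma from which to size B versus C.

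**What to change.** Extend criterion (d) to cover a personal history of colorectal cancer. If the sponsor prefers to keep enrolment wide, then at minimum record that history for every participant and keep those who have it out of group C and out of both primary ROC analyses. The general practitioner referrals and hospital electronic records named in section 3 as data sources can supply it.

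Reword (f) so that its purpose is clear and it agrees with the amended (d), and state how the lines of the inclusion list combine.

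The cost is a short amendment to the eligibility wording, one history field, and the loss of a few surveillance patients from the analysis.
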